Self-reported measurement* & cognition assessment		X			X	
Daily log		X	X	X (daily)	X	X

Pre-study adaptation night: To facilitate adaptation to sleep study procedures and a new sleep environment, the participants will report to the sleep laboratory around 8 pm on a convenient weekday. After checking in to the sleep laboratory, the research staff will provide instruction for daily log. A study schedule will be provided to the study participant (completed by a research staff). The sleep lab staff will give a tour to sleep lab. Before going to bed, the person will then be connected to the polysomnography (PSG) recording and undergo continuous PSG for one night. The recorded PSG data during the adaptation night will not be analyzed as per standard sleep research methodology.

The participants will be instructed to complete the 8 self-administered instruments, including PROMIS-Sleep Disturbance, PSQI, PROMIS-Fatigue, PROMIS-depression, CES-D, EORTC

QLQ-C30, PROMIS-Physical Function, and PSS on the day of baseline data collection (blue folder). They will be asked to return the completed instruments on their next sleep lab visit.

Starting from the adaptation night and throughout the study, the participants will complete the daily log each morning and before going to bed to record sleep/wake activities, naptimes, and levels of fatigue throughout the day.

Baseline data collection: Within a week (prefer next day), the participants will return to the sleep laboratory around 7 pm. After checking in the sleep lab), the participants will complete the NIH Toolbox Cognition Battery via iPad Air (administered by the research staff).

The participants will be connected to the PSG recording before going to bed and undergo overnight PSG monitoring. The recording for the PSG analysis will start at the time of lights out and will end at the time of final awakening in the morning (when the individual is out of bed). With the assistant from a research staff, the participant will be instructed to self-insert the thermistor just before going to bed and will remove (by herself) thermistor after final awakening in the morning. Core temperature readings will be continuously monitored and recorded every 5 minutes during the all-night sleep studies. The data at 5 minute intervals starting with lights out will be used for analysis.

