The participants will be instructed to complete the 8 self-administered instruments, including PROMIS-Sleep Disturbance, PSQI, PROMIS-Fatigue, PROMIS-depression, CES-D, EORTC QLQ-C30, PROMIS-Physical Function, and PSS on the day of posttest data collection. They will be asked to return the completed instruments on their sleep lab visit.

Post-treatment data collection: The post-treatment data collection will start on the next day after completion of the 14-day intervention protocol. Following the same protocol described in baseline data collection, the participants will report to the sleep laboratory 7 pm and then complete the MoCA and the NIH Toolbox Cognition Battery, administered by a research staff.

Before going to bed, the participants will be connected to the PSG recording at their regular bedtime hours and undergo overnight PSG monitoring. With the assistant from a research staff, the participant will self-insert the thermistor just before going to bed and will remove thermistor after final awakening in the morning. The PSG and core temperature recordings for the analysis will start at the time of lights out and will end after final awakening in the morning. During the post-treatment data collection, the participants will complete the daily log before going to bed and the following morning.

Before checking out of the sleep laboratory, the participant will return the daily log. All participants will receive an exit interview before checking out the sleep lab or within 3 days regarding issues or difficulties encountered during the study and complete a list of rating scales measuring levels of burden for study activities.

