**Effects of Bright Light on Co-occurring Cancer-related Symptoms
in Breast Cancer Survivors**

NCT03304587

PI: [name]

Statistical Analysis Plan

May 1, 2022

Statistical Analysis Plan

The data analysis of **Aim 1** will be descriptive in nature. To assess the feasibility of the proposed study protocol, the numbers of subjects contacted and screened, the proportion of eligible subjects from those contacted, the proportion of those successfully recruited from the pool of eligible subjects, the proportion retained of those recruited, completeness of the data collected, ease of using each measure, and adverse effects (if there are any) will be described using summary statistics. Adherence to treatment will be assessed by measuring timing of visor cap usage. Adherence to outcome reporting will be evaluated by estimating completion rates of scheduled PSG recordings, core body temperature measures, and self-report forms at both time periods. The proportion and the reason for missing data on each outcome will also be assessed.

The objective of **Aim 2** is to assess the effects of bright light on the 4 symptoms (sleep disturbance, fatigue, depression, cognitive dysfunction) and quality of life. Nocturnal sleep patterns will be measured objectively and subjectively. Objective sleep patterns will be monitored in a sleep laboratory by all-night PSG before and after the light intervention. The endpoints for sleep patterns (the sleep continuity measures include sleep onset latency, arousals, wake after sleep onset, and sleep efficiency) will be derived from scoring the PSG record by a polysomnographer blind to intervention assignment. Subjective endpoints for sleep patterns (sleep onset latency, sleep disturbance, and sleep efficiency) will be self-reported by participants before and after the light intervention. For each endpoint, the between-group difference will be compared using two-way ANOVA for repeated measurement data and to account for potential correlation among multiple measurements taken from the same individual. Important covariates such as ambient light and the level of stress (as measured by PSS) will be adjusted if necessary. Fatigue, depression, cognition, and quality of life will be subjectively and objectively assessed before and after the light intervention. Between-group differences in those subjective measurements will be compared using two-way ANOVA.

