The objective of **Aim 3** is to assess the effects of bright light on circadian rhythms. Circadian rhythm will be measured by nocturnal core body temperature before and after the light intervention. The phase shift of the nocturnal core body temperature will be calculated by the timing of the peak and trough of the temperature curve. To take full advantage of the availability of intensive data from continuous sleep-time core body temperature measurement, the difference in circadian rhythms between groups will also be compared using functional data analysis (FDA), a collection of emerging techniques about the analysis of information on curves or functions. Unlike the conventional methods such as ANOVA that only focus on the differences at a few fixed time points, FDA provides information about curves, surfaces, or anything else varying over a continuum. Specifically, after a proper registration or alignment of the temperature curves from each individual, FDA will allow us not only to compare the overall circadian rhythms between groups, but also correlate the curves with other measured data such as symptom scores from Aim 2. Such a curve-based analysis will allow us to compare not only the magnitude (peak and trough) but also the shift in the circadian cycle.

Mediation analysis will also be performed to better understand the possible mechanism of bright light intervention on the 4 symptoms. Specifically, functional principal component analysis (FPCA) will first be applied to core body temperature during pre- and post-treatment periods separately to identify distinct patterns of circadian rhythms. The causal-step approach outlined in the classic work of mediation analysis will then be used to estimate the direct and indirect treatment effects and to quantify the potential mediating effects of circadian rhythms. Due to relatively small sample size, the interest will focus more on the estimation and precision of mediating effects rather than significance testing.

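### Aim 3 reads overnight core temperature as circadian rhythm with no step to separate the effect of sleep and waking, so a sleep improvement can be credited to the body clock

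*SAP*

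**What the plan says.** SAP, Aim 3, equates the construct with one signal: "Circadian rhythm will be measured by nocturnal core body temperature before and after the light intervention". Neither document names a second circadian marker. The phase measure is defined as follows: "The phase shift of the nocturnal core body temperature will be calculated by the timing of the peak and trough of the temperature curve". Groups are also compared by functional data analysis after the individual curves have been registered or aligned. FPCA of the pre- and post-treatment temperature curves, done separately, then feeds a causal-step mediation analysis intended to "estimate the direct and indirect treatment effects and to quantify the potential mediating effects of circadian rhythms".

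The Protocol fixes the recording window. Under Baseline data collection: "Core temperature readings will be continuously monitored and recorded every 5 minutes during the all-night sleep studies", and "The data at 5 minute intervals starting with lights out will be used for analysis". Under Post-treatment data collection: "The PSG and core temperature recordings for the analysis will start at the time of lights out and will end after final awakening".

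The PSG on those nights supplies the objective sleep endpoints of SAP Aim 2: onset latency, arousals, wake after sleep onset and sleep efficiency. The mediation paragraph takes the symptoms as outcomes, and Aim 2 lists these among "the 4 symptoms (sleep disturbance, fatigue, depression, cognitive dysfunction) and quality of life". The only covariates named in the SAP are ambient light and stress. They appear in the Aim 2 paragraph and are to be used only if needed.

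**The concern.** Core temperature falls with sleep and rises with waking. This is general physiology; the documents neither state it nor give a size. The trial asks whether light improves sleep. If it does, the groups will differ in sleep/wake state during the very minutes in which temperature is read, and their temperature curves can then differ although the clock has not moved.

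Randomisation does not remove this, because the difference in sleep arises after allocation and is itself an intended effect of treatment. The artefact grows with success in Aim 2.

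Two conclusions are at stake. Aim 3 could report a circadian difference that is really the Aim 2 sleep difference. The mediation analysis could also assign part of the treatment effect to circadian rhythm when it runs through sleep. The PSG that could help to tell the two apart is recorded on the same nights but is not used for this.

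**Working it through.** **No plan figure to reproduce.** The documents give no sample size, effect size, variance or temperature response for Aim 3. The question is therefore whether the planned kind of analysis can return a circadian effect when none exists.

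**Inputs from the documents.** Readings every 5 minutes from lights out to final awakening; one night before and one after treatment; phase from peak and trough timing; FPCA scores as mediator.

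**Assumed inputs.**
- Window 8 h, so 480/5 = 96 readings.
- Group effect on circadian phase, amplitude and level: zero.
- Light shortens onset latency by 20 min and wake after sleep onset by 45 min. Sleep efficiency then improved by 10.0 to 11.6 points in the simulated data.
- Sleep lowers temperature by m = 0.1, 0.2 or 0.3 C, with a 45-min exponential lag.
- Wake is spread over the night, or confined to the last 3.5 h.
- Each person's temperature level is stable between nights, or varies by night with SD 0.05 C.

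**Formulas.** The false difference in nightly mean is roughly −m × (change in fraction of night asleep). For m = 0.1 and 11.4 points this is −0.1 × 0.114 = −0.011 C, which matches the simulation. The false mediated share is 1 − c′/c. Here c is the group effect on change in sleep efficiency, and c′ is the same effect after adding the first three principal components of the post-minus-pre temperature curve.

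**Results.** Shifts and shares use 4,000 per group. Rejection rates use 25 per group (assumed), 400 replicates and a t-test on change scores.

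| Wake | Nightly SD (C) | m (C) | Mean diff. (C) | Rejection, mean | Trough shift (min) | Rejection, trough | False mediated share |
|---|---|---|---|---|---|---|---|
| spread | 0 | 0.1 | −0.011 | 97% | 0.0 | 3.5% | 0.24 |
| spread | 0 | 0.2 | −0.022 | 100% | 2.0 | 5.0% | 0.40 |
| spread | 0 | 0.3 | −0.032 | 100% | −3.2 | 4.5% | 0.49 |
| spread | 0.05 | 0.1 | −0.010 | 8% | 0.1 | 3.5% | 0.01 |
| spread | 0.05 | 0.2 | −0.020 | 22% | −3.1 | 5.0% | 0.02 |
| spread | 0.05 | 0.3 | −0.030 | 34% | −3.5 | 4.5% | 0.04 |
| late | 0 | 0.1 | −0.009 | 92% | 10.6 | 19.5% | 0.33 |
| late | 0 | 0.2 | −0.017 | 100% | 19.8 | 27.3% | 0.56 |
| late | 0 | 0.3 | −0.027 | 100% | 24.9 | 29.0% | 0.68 |
| late | 0.05 | 0.1 | −0.011 | 8% | 12.3 | 19.5% | 0.01 |
| late | 0.05 | 0.2 | −0.020 | 18% | 18.3 | 27.3% | 0.04 |
| late | 0.05 | 0.3 | −0.029 | 29% | 22.8 | 29.0% | 0.08 |

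With m = 0, rejection was 3% to 6% and the mediated share was 0.00 throughout, so the effect comes from the sleep term alone.

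**Hand check of the nightly-variation rows.** Nightly variation alone gives a change-score SD of 0.05 × √2 = 0.071 C. The standard error at 25 per group is 0.071 × √(2/25) = 0.020 C. False differences of 0.010, 0.020 and 0.030 C are therefore 0.5, 1.0 and 1.5 standard errors. At the two-sided 5% level these imply rejection of about 8%, 17% and 32%, in line with the table.

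**Other assumed settings.** A second run used 3,000 per group, latency 20 min shorter, wake 30 min less, m = 0.1 to 0.3 C and a 30-min lag. The false share was 12% to 57% with stable level and 4% to 18% with nightly SD 0.05 C. A third run, again with no clock change, gave 28% to 77% and 2% to 16%.

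**Does adjustment help?** In the second run, adding wake lagged by 0 to 60 min cut the false share to 0% to 1.3% and the false temperature difference to at most 0.10 SD. With a true 30-min phase advance added (m = 0.2 C), the true temperature difference was −0.0126 C, the adjusted estimate −0.0133 C and the unadjusted estimate −0.0283 C.

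**Limits.** The mediation calculation used change curves, whereas the SAP runs FPCA separately before and after treatment. No registration step was simulated. Peak timing was not assessed.

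**The case against.** Several stronger readings are tempting, and the documents do not support them.

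- *The SAP compares raw curves.* It does not: the functional comparison follows registration or alignment. The alignment target is not given, however. Alignment acts on timing and does not remove a difference in level caused by sleep.
- *Better sleep would pass for a phase advance.* The SAP reads phase from peak and trough. With wake spread over the night, the false trough shift stayed within 3.5 min and rejection was near nominal. Where the trough did move (wake late in the night), it moved later. An earlier falling limb is possible but is not the SAP's stated phase measure.
- *Sleep becomes a mediator of itself.* The mediation paragraph refers to the four symptoms and does not say that PSG endpoints are the outcomes. The questionnaires are completed on the day of post-treatment collection, and cognition is tested after the 7 pm arrival, so neither is a product of that night's sleep. The charge is literal only if same-night PSG endpoints are used. For the other outcomes, the risk is that an effect running through improved sleep is labelled circadian.
- *The mediation analysis would report a spurious mechanism.* The SAP speaks cautiously of possible mechanisms, and it prefers estimation and precision to testing because the sample is small. That tempers the claim, but a precise estimate can still be biased.

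Two further objections stand. All sizes are assumed, and with realistic nightly variation the artefact may be small. Adjusting for PSG wake also conditions on a post-treatment variable and may remove part of a true clock effect that acts together with sleep.

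**Conclusion.** The concern holds in a limited form. Followed exactly, the plan has no step that stops a sleep improvement from appearing as a circadian difference in the level, shape or FPCA scores of the temperature curve, or from being credited to circadian rhythm in the mediation analysis. Trough timing is little affected unless waking is concentrated late in the night.

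The size cannot be fixed from the documents. With zero true circadian change, the false mediated share for sleep efficiency ran from 1% to 77% across the settings tried. The two main drivers are night-to-night variation in temperature level and the size of the sleep effect. For a fatigue score made to depend only on sleep, the share was similar: 0.28 to 0.69 with stable level and 0.01 to 0.08 with nightly SD 0.05 C. The conclusion rests on the physiological premise that sleep state moves temperature; without it the artefact is nil.

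**What to change.** 1. Keep the planned Aim 3 analysis. Add a companion FDA/FPCA comparison with 5-minute PSG sleep/wake state (concurrent wake and wake lagged by 0 to 60 min) as a time-varying term, and report both. Where a level or shape difference appears only without adjustment, describe it as a difference in the nocturnal temperature profile that cannot be separated from sleep.
2. If same-night PSG endpoints are used as outcomes in the temperature mediation, report those results as association only, not as an indirect effect.

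The cost is some extra analysis and the time-aligning of two recordings. The Protocol gives them a common lights-out start but does not say that they share a clock. No new visit, device or participant burden is needed. The adjustment performed well in simulation, but there the lag window covered the simulated lag; real data may be less favourable. Because the adjusted estimate may also lose part of a true effect, neither version should serve as a pass/fail rule for calling a difference circadian.

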If the candidate agrees to be approached, the investigator/research assistant will contact the candidate over the telephone. The topic and the purposes of the study will be introduced. If the candidate is interested, the investigator/research assistant will schedule the visit for recruitment/consent. (Script is followed)

The recruitment/consent visit will be either on the day of the individual's convenience. The investigator/research assistant will provide explanation of the screening, the study procedures involved, the time commitment, and the purpose of written consent. Also, the candidates will be told that phone calls will be made during the study period. Potential subjects will be instructed to read the consent forms carefully. Any questions will be answered before signing. Before written consent is obtained, no personal information will be revealed or recorded. (Pink folder)

After giving informed consent, candidates will first complete the demographic information and 4 self-administered screening tools including the Horne-Ostberg Morningness-Eveningness Questionnaire (MEQ), the International Statistical Classification of Diseases and Related Health Problems (10th revision) (ICD-10) criteria for cancer-related fatigue, Pittsburgh Sleep Quality Index (PSQI), and the Center for Epidemiological Studies Depression Scale (CES-D). A research staff will instruct the participant and administer the Montreal Cognitive Assessment (MoCA) with paper and pencil. After that, candidates will then be individually screened/interviewed for the exclusion criteria (scoring criteria provided). Those who met the study criteria will be scheduled of the study activities (Blue folder).

Participants will be enrolled in the study for approximately 3 weeks. Each participant will make 3 overnight visits to the sleep laboratory. The research protocol consists of a pre-study adaptation night, baseline data collection, 14-day treatment phase, and post-treatment data collection. Night-time Sleep patterns and overnight core body temperature will be monitored in a sleep laboratory before and after the bright light intervention.

	Pre-Study	Baseline		Treatment	Post-Treatment	
Study Day	(prior baseline)	D1	D2	(14 consecutive days)	D1	D2
Bright light protocol				X (daily)		
Polysomnography (overnight only)	Adaptation night	X	End		X	End
Core body temperature (overnight only)	Adaptation night	X	End		X	End

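### Aim 3 takes phase shift partly from peak timing, but temperature is recorded only from lights out to final awakening, so the recorded peak mostly marks bedtime or wake time

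*SAP*

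**What the plan says.** The SAP, under Aim 3, gives one explicit definition of phase shift: "The phase shift of the nocturnal core body temperature will be calculated by the timing of the peak and trough of the temperature curve". It does not say how peak and trough are combined, which counts if they disagree, what curve is fitted, or what happens when an extreme falls on the first or last reading.

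The Protocol limits the record to the night. The schedule table under Procedures lists "Core body temperature (overnight only" among its measurements. At baseline the participant will "self-insert the thermistor just before going to bed and will remove (by herself) thermistor after final awakening in the morning", and "The data at 5 minute intervals starting with lights out will be used for analysis". Post-treatment, the "core temperature recordings for the analysis will start at the time of lights out and will end after final awakening". No evening or daytime temperature is collected.

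On the post-treatment night participants are "connected to the PSG recording at their regular bedtime hours", which sets no clock time for lights out.

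The SAP adds a functional data analysis of the same night-time curves, carried out "after a proper registration or alignment of the temperature curves from each individual".

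**The concern.** A phase marker has to move with the body clock and stay still when only sleep timing moves. If the record stops before the temperature peak can occur, its highest value is wherever the record happens to start or end. The peak half of the measure would then miss a real circadian shift, and would report an earlier bedtime and awakening as a circadian advance.

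Sleep is an Aim 2 outcome, and the light may change it, so bed and wake times could differ between arms after treatment. A between-arm difference in recorded peak time could then appear with no circadian effect behind it. Because the SAP does not say how peak and trough are combined, the faulty half could also contaminate the usable half.

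**Working it through.** The documents give no sample size, effect size or expected phase shift for Aim 3, so there is no figure to reproduce. The recording window, the 5-minute interval and the peak-and-trough definition come from the documents. Every other input below is an assumption. Negative shifts mean earlier.

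**Geometry.** Take T(t) = M - A cos(2π(t - τ)/24), with trough at τ and peak at τ + 12 h. A record shorter than 12 h that contains τ cannot contain the peak. Temperature falls from lights out to τ and rises from τ to awakening, so the maximum lies at whichever end is farther from τ.

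Example: an 8-h record, trough 5 h after lights out, A = 0.4 C.
- At lights out: -0.4 × cos(75°) = -0.10 C relative to M.
- At awakening, 3 h after the trough: -0.4 × cos(45°) = -0.28 C.
- The recorded peak is therefore lights out.

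| Change on the second night | Recorded peak moves | Trough moves |
|---|---|---|
| True shift -2 h | +8 h (jumps to awakening) | -2 h |
| True shift -1 h | 0 (the two ends tie; first reading taken) | -1 h |
| True shift -0.5, +0.5, +1 or +2 h | 0 | exact |
| Lights out -1, -0.5, +0.5 or +1 h, awakening and phase fixed | same as lights out | 0 |

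The +8 h jump shows how a mean can take the wrong sign: when an advance carries a woman's trough past mid-record, her recorded peak moves from lights out to awakening.

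**Main simulation.** There were 864 combinations with 500 women each. Lights out was 23:00 (SD 0.5 h), trough SD 1 h, and mean trough 04:00, 05:00 or 06:00. The other inputs were:
- 7 or 8 h in bed;
- amplitude 0.3-0.5 C;
- noise SD 0.03-0.10 C, independent or autocorrelated (rho 0.9);
- peak-to-trough fall of 8 or 12 h;
- 35- or 65-minute moving average;
- sleep-onset drop of 0 or 0.3 C.

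Peak results:
- The maximum lay within 30 min of an end on 54-100% of baseline nights, and on at least 80% in 93% of combinations. Of the 62 lower combinations, 60 had 0.10 C noise.
- True 60-min advance, same bedtime: median shift -5 to +40 min, and 0 in 95% of combinations. The mean was -10 to +167 min, above zero in 74%.
- No circadian change, lights out and awakening 60 min earlier: median shift -45 to -70 min, and -60 in 94%.

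Trough results (middle 90% of combinations):
- True 60-min advance: median -35 to -60 min with a mean trough at 04:00-05:00, and -15 to -50 at 06:00.
- Lights out and awakening 60 min earlier only: -5 to -43 min at 04:00-05:00, and -30 to -60 at 06:00.
- SD of change per woman: 32-101 min (full range over all combinations 18-136).

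A separate 48-combination simulation with inputs in the same range agreed. The maximum was within 30 min of an end on 68-100% of nights. A true 60-min advance gave a median peak shift of 0 to +15 min and a trough shift of -20 to -60. A 60-min earlier bedtime alone moved the median peak by -60 to -65 min.

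**Fitted peaks** (8-h record, 24 combinations, 800 women each). A one-harmonic cosine put the peak exactly 720 min from its trough every time, so it adds no information. A two-harmonic fit must extrapolate: its peak had an SD of change of 47-374 min with no true change, and moved -15 to -55 min with bedtime alone.

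**The case against.** The plan has four defences, and none rescues peak timing.
- The peak may mean only the night's maximum. That is the quantity simulated, and it tracks the ends of the record.
- A fitted curve might locate the peak. None is specified, and the fits above do not help.
- The functional analysis also addresses shift. It uses the same night-time curves, so it cannot supply the missing hours, although it does remain as an additional analysis.
- Regular bedtimes limit drift. They do, but they do not fix lights out to a clock time.

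Four criticisms of the size of the claim deserve weight.
- The wrong-sign result is less stable than the missed-effect result. In a 48-combination check, about a third of combinations had a mean wrong-way shift of 10 min or less. The firm statement is that the peak misses the shift; the wrong sign depends on trough position.
- The 60-min bedtime change is a stress test, and a false treatment effect needs the arms to change differently. With a 15-min change, the median false peak shift was 15 min and the false trough shift 0-15 min.
- The Protocol gives light either soon after waking or in the early evening, so delays matter too. For a true 60-min delay the trough moved only +10 to +55 min, because a later trough runs into the end of the record. The sign is right, but the effect is attenuated. This limits the replacement measure; it does not defend the peak.
- The minute figures depend on assumed inputs, including the sleep-onset drop. The test of the fix used large arms, whereas the SAP itself describes a small sample, and the loss of precision from adjustment was not assessed.

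**Conclusion.** The concern holds. As written, one of the two components of the phase-shift measure mostly records when the woman went to bed or woke. This follows from the recording window in the Protocol, given a 24-h rhythm with a night-time trough and a record shorter than 12 h. Confidence in that geometry is high; the exact minutes are conditional on the assumed ranges.

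The trough is the better marker because it moves in the correct direction with true phase. It is attenuated, noisy, partly dependent on sleep timing, and weakest when it falls near awakening. The trough and curve analyses remain, so this is a defect in one named measure that should be corrected, and it does not invalidate Aim 3.

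**What to change.** In SAP Aim 3, define phase as the clock time of the trough of a smoothed temperature curve, name the smoother, and remove peak timing as a phase measure. That is the essential edit. In support of it:
- Report, by arm and period, nights whose minimum lies within 30 min of either end of the record. Run the analysis with and without them, noting that flagging can differ by arm.
- Report the change in lights-out and awakening times by arm.
- Add a sensitivity analysis of trough change, either adjusted for those two changes or restricted to the clock-time window that both of a woman's nights cover. Both times are measured after treatment starts, so this should not be primary.
- As clarification only, state the registration method and time axis for the functional analysis. Take the shift from unregistered clock-time curves or from the per-person alignment shifts.

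**Cost.** SAP wording and minor code. No new data are needed, because the Protocol already bounds the sleep record by these times: "The recording for the PSG analysis will start at the time of lights out and will end at the time of final awakening". The peak measure is lost, and some nights have a poorly estimated trough.

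The fix was tested in 48 combinations with 1,000 women per arm and individual bedtime changes of SD 30 min (amplitude 0.4 C, 12-h fall and 35-min average held fixed):
- Bedtime 60 min earlier, no circadian change: false trough difference -4 to -42 min (median -25) unadjusted, -11 to +14 (median 0) adjusted, and -7 to +7 with the shared window.
- True 60-min advance, bedtime unchanged: -20 to -63 min unadjusted and -19 to -63 adjusted, median -45 in both.
- True 60-min advance with bedtime 30 min earlier: median -43 min adjusted against -52 unadjusted. Here the adjusted value lies farther from -60, which is a further reason to keep adjustment as sensitivity.
- At least one flagged night: 3-79% of women in an arm that advances 60 min and 4-86% in one that does not (median gap 7 points), highest with a 06:00 trough. Excluding flagged women changed the estimated advance little (median -44 against -45 min).
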